4.4 Handling of Dropouts or Missing Data

Missing values will not be substituted by estimated values, but treated as missing in the statistical evaluation, except missing data imputation for WOMAC subscale scores, which is detailed in Section 4.6. All data from all subjects dosed in the study will be included in all listings, plots, and statistical analyses when appropriate.

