Both formulations at either strength were well tolerated and reduced OAKP by 75% or more compared to baseline. Analgesic effect persisted to Day 33 (last follow up day). No serious adverse events (SAEs), no adverse events (AEs) resulting in subject discontinuation or subject requested withdrawal, only AEs that were possibly, probably or definitely treatment related were: (a) local at the application site and Rheumatology Common Toxicity Criteria (RCTC) toxicity grades were generally 1 (mild) and at highest 2 (moderate) and were mostly BSP with less frequent erythema, pruritus, and scaling (latter only for CGS-125-10); and (b) coughing / sneezing during or following application (RCTC Grade 1, mild) which was observed in a higher proportion of CGS-125 subjects (40% - 60%) than in CGS-200 subjects (20% - 27%). Comparison of Day 33 (study exit) values for serum chemistry and hematology with values at screening showed no remarkable changes in any subjects and no differences for any subject, comparing Day 33 to Screening, that were atypical of the normal variations in serum chemistry and hematology values in individuals for blood sampling at different time points. In summary, no suggestion of systemic toxicities related to treatment was observed.

In Study VZU00021 neither vehicle or a true placebo was used as the study was designed to compare the CGS-200 formulation with the CGS-125 formulation in terms of tolerability and efficacy for a 4-day, once daily for 1-hour treatment regimen.

Study VZU00023

This was a vehicle-controlled study of safety, tolerability and efficacy of CGS-200 5% capsacian in subjects with OA of the knee. Single daily application for four consecutive days with 93 days (13 weeks) follow up.

CGS-200-5 was well tolerated and reduced OAKP at 13 weeks by 93% compared to baseline. No SAEs, no AEs resulting in subject discontinuation or subject requested withdrawal, only AEs that were possibly, probably or definitely treatment related were: (a) local at the application site and RCTC toxicity grades were generally 1 (mild) and at highest 2 (moderate) and were mostly BSP (in 100% of subjects) with less frequent erythema (72% of subjects), and pruritus (56% or subjects); and (b) coughing / sneezing during or following application (RCTC Grade 1, mild) which was observed in 20% of subjects. No suggestion of systemic toxicities related to treatment was observed.

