5.2 CONCURRENT MEDICATIONS

5.2.1 Allowed Regimens

Subjects may continue their baseline medication(s) as long as the medications are not prohibited as outlined in Section 5.2.2. If for any reason deemed necessary by the investigator, a subject requires additional medication(s) or change of dose, the medication(s), dosage change, route of administration, start and stop dates, and the indication for which it was given must be recorded in the source documents and electronic case report form (eCRF).

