6.8 CONCOMITANT MEDICATIONS/RESCUE MEDICATIONS

Subjects may continue their baseline medication(s) as long as the medications are not among the prohibited medications listed in Section 5.2.2. The daily dose of each medication should be maintained throughout the study since any changes to this background regimen may have an effect on the assessment. Subjects are allowed to increase dosage of NSAIDs or use analgesics to treat minor pain throughout the study, provided all concomitant medications are back to baseline dosages within 24 hours of a clinical assessment visit.

If for any reason deemed necessary by the investigator, such as in the event of a substantial disease flare which cannot be treated with increased drugs (NSAIDs) or narcotic, a rescue medication can be initiated at any time that is in the best interests of the subject. Rescue medication should be carefully considered by the principal investigator (PI) since there may be an effect on the results of the study. All changes and start and stop dates, and the indication for which it was given must be recorded in the source documents and eCRF. Routine changes (dose, route, etc.) to the background treatments should not be performed.

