3.2.4 Subject Compliance

Subjects will be free to withdraw from treatment or from the study at any time for any reason, or they may be withdrawn/removed, if necessary (see reasons for withdrawal below). It is understood by all concerned that an excessive rate of withdrawals can render the study uninterpretable; therefore, unnecessary withdrawal of subjects should be avoided.

Subjects will be removed from treatment for the following reasons:

- Unacceptable acute toxicities defined as:
 - Occurrence of a Dose-limiting toxicity (DLT)

Subjects will be removed from the study for the following reasons:

- Withdrawal of consent
- Non-compliance/Lost to follow-up
- Pregnancy

If treatment with study drug is interrupted and permanently stopped, subjects should remain on study and will be followed for scheduled safety and study assessments through Day 35. If the subject goes onto other treatment, this should be noted in the source documents and the concomitant medications electronic case report form (eCRF).

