4.2 Analysis Sets

The following three analysis sets will be defined for this study:

The intent-to-treat (ITT) set will be defined as all randomized subjects, whether or not they receive study drug.

The modified ITT (mITT) set will be defined as the subset of the ITT subjects that receive at least one dose of study medication and have at least one evaluable post-dosing efficacy endpoint. The mITT set will be defined based on randomized treatment rather than treatment actually received.

All efficacy analyses will be carried out using the mITT set.

The safety (SAF) set will be based on the ITT subjects who have received at least one dose of study medication (based on the treatment actually received rather than randomized treatment). All safety analyses will be carried out using the SAF set.

The Per Protocol (PP) set will include all mITT subjects in whom there were no major protocol deviations. Major protocol deviations for defining the PP analysis set will be identified by Vizuri prior to the database lock. If deemed appropriate, the analyses on primary and secondary efficacy endpoints listed in Section 6.1 and 6.2 will be repeated using the PP set.

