4.6 Data Derivations and Transformations

The WOMAC is composed of 3 subscales (A: Pain, B: Stiffness, C: Physical Function). Each subscale contains components that are scored using VAS ranging from 0 to 100 mm to capture the subject's response to each of the questions. There are 5 components for subscale A (Pain), 2 components for subscale B (Stiffness), and 17 components for subscale C (Physical Function).

A WOMAC subscale score is calculated by adding the component scores within the subscale. The total WOMAC score is computed as the sum of the 3 WOMAC subscale responses. In the case of missing data for a component of the WOMAC subscale, the average score of the non-missing components within the subscale will be used to impute for the missing values. However, the subscale score will be set to missing according to the following criteria: if ≥ 2 Pain components are missing, if both Stiffness components are missing, if ≥ 4 Physical Function components are missing. The total WOMAC score will be set to missing if any of the WOMAC subscale scores are set to missing.

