6.1 Primary Efficacy Endpoint and Analysis

The primary efficacy endpoint is the change from baseline in WOMAC pain score at Day 35. WOMAC pain score reduction at Day 35 will be evaluated using the “Study Knee”.

Change from baseline in WOMAC pain score on the Study Knee between each Active Treatment Arm and the Vehicle Arm at Day 35 will be evaluated using analysis of covariance (ANCOVA) model. The ANCOVA model will be fitted with the treatment as a fixed effect, baseline value as a covariate and treatment-by-baseline interaction. The adjusted group mean (least squares mean) changes will be compared at a 2-sided significance level of 0.05. The *p* value along with the 95% confidence interval for the treatment difference will be reported.

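### The primary Day 35 ANCOVA leaves out the Day 5 and Day 19 scores of subjects with no Day 35 WOMAC pain score, and no missing-data sensitivity analysis of the primary endpoint is planned

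*SAP*

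**What the plan says.** SAP 6.1 defines the primary endpoint as change from baseline in Study Knee WOMAC pain at Day 35. The comparison of each active arm with vehicle "at Day 35 will be evaluated using analysis of covariance (ANCOVA) model", with treatment, baseline and their interaction as terms. No other visit enters.

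SAP 4.4 sets the missing-data rule: "Missing values will not be substituted by estimated values, but treated as missing in the statistical evaluation, except missing data imputation for WOMAC subscale scores". Protocol 9.5.8 has the same rule without the exception. SAP 4.6 explains the exception: "the average score of the non-missing components within the subscale will be used to impute for the missing values". It acts within one visit, and the pain score is missing once two of its five items are missing.

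SAP 4.2 admits to mITT subjects who "receive at least one dose of study medication and have at least one evaluable post-dosing efficacy endpoint". A Day 35 score is not required.

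Three other provisions come close but do not fill the gap. The per-protocol repeat in SAP 4.2 is optional and only narrows mITT. SAP 6.3 counts a missing score as failure, but only in the responder tabulation. SAP 6.4 allows post hoc tests without naming one.

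Replacement is covered in the Protocol synopsis, Protocol 4.2 and SAP 3.2.1: up to 10 subjects per arm. The first sentence of the rule excludes those who leave for lack of tolerability. A later sentence, on loss between Day 5 and Day 35, states no such limit.

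**The concern.** An analysis restricted to observed Day 35 scores is unbiased if the chance of a missing score depends only on arm and baseline. If it depends on how the subject was doing at Day 5 or Day 19, the subjects left at Day 35 are a selected group. When selection differs between arms, the contrast shifts. It moves toward zero if poor responders leave in all arms and the drug works, or leave mainly on vehicle. It moves away from zero if they leave mainly on active treatment.

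The scores that would correct for selection on observed response are already scheduled. The plan does not use them in the primary contrast, and nothing planned would show how far the result rests on the assumption.

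**Working it through.** **1. The plan's own figure.** SAP 9: 40 per arm, difference 63, SD 100, two-sided 5%. SE = 100 × √(2/40) = 22.4. Power = Φ(63/22.4 − 1.96) = Φ(0.86) = 80.4% (79.5% by noncentral t). The stated 80% reproduces for 40 observed subjects per arm.

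**2. Assumptions not in the documents.** Mean effects 0, 31.5 and 63 on vehicle, 1% and 5%, equal at each visit. Correlation between visits 0.7; correlation of change with baseline −0.3. Loss after Day 19 of 5, 10 or 20% overall, logistic in the observed Day 19 score, with slope 1 or 2 logits per 100 points. These slopes are odds ratios of e¹ = 2.7 and e² = 7.4. For scale, 20% is the whole allowance (10 of 50); it is not a forecast.

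**3. Direct calculation, ignoring baseline.** Let s be the mean Day 19 change among stayers minus that among all subjects in an arm. With equal SDs, the Day 35 mean among stayers shifts by 0.7 × s. So the estimate ≈ 63 + 0.7 × (s_vehicle − s_5%). Numerical integration at 20% loss gives:

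- Odds ratio 2.7: loss 24% on vehicle v 16% on 5%; s = −20.9 and −13.9. Estimate = 63 + 0.7 × (−7.0) = 58.1.
- Odds ratio 7.4: loss 27% v 14%; s = −33.8 and −18.8. Estimate = 63 + 0.7 × (−15.0) = 52.5.

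**4. Simulation with the SAP model** (3,000 trials per case, 40 randomised per arm, Monte Carlo error about 0.4 points), same mechanism in all arms:

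| Odds ratio per 100 points | Loss | ANCOVA | Repeated measures |
|---|---|---|---|
| 2.7 | 5 / 10 / 20% | 61.8 / 60.1 / 59.0 | 63.4 / 62.8 / 63.2 |
| 7.4 | 5 / 10 / 20% | 58.8 / 57.1 / 53.8 | 62.8 / 63.2 / 62.9 |

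Across this and repeat runs, ANCOVA ranges over about 58–62 and 53–60. The largest bias, 63 − 53 = 10, is under half of 22.4.

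**5. Sensitivity to the assumptions.**

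- At correlation 0.5, the most extreme case (20%, odds ratio 7.4) gives 57.
- If loss depends on the score relative to the subject's own arm, s is equal in both arms and ANCOVA gives about 63.
- If outcome-related loss is confined to vehicle, ANCOVA falls below 63 (61 down to 47). If confined to active treatment, it rises above 63 (65 up to 79). This shows that the sign is open. The far ends need 20% loss and the 7.4 odds ratio, and nothing in the documents suggests one-arm loss.

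**6. Power with replacement.** With 42, 44 and 50 randomised per arm at 5, 10 and 20% loss, about 40 are observed. ANCOVA power at the 2.7 odds ratio is then 81, 79 and 78%; repeat runs gave 79 to 81%. Numbers are restored; the bias in step 4 stays.

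**7. Limits of repeated measures.**

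- Loss before Day 5 driven by the unseen Day 5 score: no gain (54–61 with either method), because WOMAC is not scheduled on Days 2–4 (SAP Appendix A, footnote j).
- Loss driven by the unseen Day 35 value: partial gain (49–60 v 56–61).

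**The case against.** The strongest case against is that substantial loss is not shown and the study is built to limit it. Dosing lasts four days. Those who stop study drug are retained: "subjects should remain on study and will be followed for scheduled safety and study assessments through Day 35". A poor responder need not leave to get relief: "Subjects may continue their baseline medication(s) as long as the medications are not prohibited" (Protocol 5.2.1) and "Subjects are allowed to increase dosage of NSAIDs or use analgesics to treat minor pain throughout the study" (Protocol 6.8). Protocol 1.3 reports, for VZU00021, "no adverse events (AEs) resulting in subject discontinuation or subject requested withdrawal", and says the same for both arms of VZU00023. SAP 4.5 calls the study exploratory, and disposition and n by visit are tabulated by arm (SAP 5.1 and 6.2).

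All of this stands and lowers the priority, but it does not close the gap. Retention of treatment stoppers does not cover withdrawn consent or loss to follow-up. The earlier studies were run in the Dominican Republic, and the text does not report missed visits. Tabulating the loss shows it without adjusting the estimate. Exploratory status is invoked for multiplicity, not for bias.

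Two stronger readings are tempting. A reader might infer that missing Day 35 scores leave the trial well short of 80% power. That treats 40 as the number randomised. The plan is for 40 evaluable subjects per arm with replacement, and step 6 shows power of about 80%. A reader might also infer that the result will be biased by a known amount or in a known direction. In VZU00023, burning-stinging pain was reported by 100% on CGS-200-5 and 35% on vehicle, and tolerability dropouts are outside the first replacement clause, so loss could differ by arm. The documents do not show that it will.

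**Conclusion.** The point holds in a limited form. The primary contrast uses only mITT subjects with a Day 35 score, ignores the early scores of the rest, and has no missing-data sensitivity analysis. Replacement addresses numbers, not selection. Under the common-mechanism assumptions the bias is roughly 1 to 10 points on a difference of 63. It is smaller at lower visit correlation and about nil if loss depends only on standing within the arm. All of these figures rest on assumed dropout models, because the documents give no rate. The priority lies between worth considering and recommended: the change is cheap and uses data already scheduled, but the design keeps the likely exposure modest.

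**What to change.** In SAP 6.1, take the Day 35 contrasts from a mixed model for repeated measures on change in Study Knee WOMAC pain at Days 5, 19 and 35. Terms: treatment, visit, treatment-by-visit, baseline and baseline-by-visit, with unstructured covariance and a named fallback. Say whether the present treatment-by-baseline term carries over. Report the present ANCOVA beside it. If the sponsor prefers to keep the ANCOVA as primary, prespecify this model as the sensitivity analysis.

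Stop the model at Day 35. Protocol 9.5.7 plans analyses at Days 19, 35 and 64. In a check of a five-visit model, subjects who returned at Day 64 moved the Day 35 contrast by up to 3.1 points, so the primary result could change between analyses.

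Add one delta-adjusted (tipping-point) analysis with the shift varied by arm, since repeated measures only partly corrects loss driven by unseen values. State how an early-termination WOMAC score (Protocol 6.5) is assigned to a visit, because SAP 4.3 uses the visit as recorded.

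Cost: SAP wording, modest programming and a covariance fallback rule; no new data. A missing-at-random assumption remains, though a weaker one than the present analysis needs. Loss before Day 5 is not repaired, apart from any early-termination score assigned to a visit.

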4.5 Multiple Comparisons

Because of the exploratory nature of this study, there will be no adjustment for multiple comparisons. Therefore, individual statistically significant comparisons among the three treatments for any of the outcome measures should be interpreted with caution.

4.6 Data Derivations and Transformations

The WOMAC is composed of 3 subscales (A: Pain, B: Stiffness, C: Physical Function). Each subscale contains components that are scored using VAS ranging from 0 to 100 mm to capture the subject's response to each of the questions. There are 5 components for subscale A (Pain), 2 components for subscale B (Stiffness), and 17 components for subscale C (Physical Function).

A WOMAC subscale score is calculated by adding the component scores within the subscale. The total WOMAC score is computed as the sum of the 3 WOMAC subscale responses. In the case of missing data for a component of the WOMAC subscale, the average score of the non-missing components within the subscale will be used to impute for the missing values. However, the subscale score will be set to missing according to the following criteria: if ≥ 2 Pain components are missing, if both Stiffness components are missing, if ≥ 4 Physical Function components are missing. The total WOMAC score will be set to missing if any of the WOMAC subscale scores are set to missing.

5. STUDY SUBJECTS

5.1 Disposition of Subjects

A table of frequency counts and percentages of all screened subjects will be provided. Subject disposition including screen failures, subjects enrolled, study completion status, study medication completion status, and reasons for early termination will be tabulated by treatment group and overall. A by subject listing will also be provided.

5.2 Protocol Deviations

Distribution for the types of protocol deviations and the number of subjects that deviate from the protocol will be tabulated for the treatment groups in the ITT analysis set. A listing of all protocol deviations will be provided.

5.3 Demographic Characteristics

Descriptive statistics will be used to summarize the demographic characteristics (age, gender, race, ethnicity, height, weight, and Body Mass Index (BMI)) for the ITT analysis set. A by subject listing will also be provided.

5.4 Baseline Characteristics

Baseline characteristics of ITT subjects include electrocardiogram (ECG), serum and urine pregnancy tests, follicle-stimulating hormone (FSH) test, erythrocyte sedimentation rate (ESR), IgM Rheumatoid Factor (RF), and exploratory assessment of OAKP. Clinical laboratory test and ECG results will be summarized using descriptive statistics for each treatment group. OA average and worst daily knee pain assessment for each knee will be provided in a listing. The knee pain scales will also be summarized by Study Knee and Non-study Knee using descriptive statistics for each treatment group.

5.5 Medical History

All medical conditions and surgical procedures will be classified by system organ class (SOC) and preferred term (PT) using the Medical Dictionary for Regulatory Activities (MedDRA). The number and percent of subjects with each medical condition and surgical procedure will be presented for each SOC and PT for the ITT analysis set.

5.6 Prior and Concomitant Medications

All concomitant medication collected from screening through the end of the study will be classified

by drug class and preferred terms according to the World Health Organization (WHO) Drug Dictionary. Prior medications are any medications taken prior to the first dose of study medication (i.e., start date and end date occurs before the first study medication dose date). If the medication start date is completely missing, then the medication will be considered as concomitant unless it can be determined that the medication end date occurred prior to the first dose of study medication. If the medication start date is partially missing and the partial date is not sufficient to determine if the medication was taken after the first dose of study medication, then the medication will be considered concomitant for the study unless it can be ruled out by the partial date and/or medication end date.

The number and percent of ITT subjects using concomitant medications will be tabulated by default Anatomical, Therapeutic, and Chemical (ATC) class and by preferred name. All prior and concomitant medications will be listed. Indication for the medications used to treat OAKP will also be presented in the listing.

6. EFFICACY AND TOLERABILITY ANALYSES

All efficacy analyses will be carried out on mITT subjects. Tolerability analysis will be based on the safety analysis set. Only one knee will be indicated as the “Study Knee” for efficacy analyses. The Study Knee will be the knee with the highest WOMAC pain score at baseline. If both knees have equal WOMAC pain scores at baseline, then the right knee will be considered the Study Knee with regard to WOMAC pain and VAS pain score reduction. Data from both knees will be presented in the listings.

6.1 Primary Efficacy Endpoint and Analysis

The primary efficacy endpoint is the change from baseline in WOMAC pain score at Day 35. WOMAC pain score reduction at Day 35 will be evaluated using the “Study Knee”.

Change from baseline in WOMAC pain score on the Study Knee between each Active Treatment Arm and the Vehicle Arm at Day 35 will be evaluated using analysis of covariance (ANCOVA) model. The ANCOVA model will be fitted with the treatment as a fixed effect, baseline value as a covariate and treatment-by-baseline interaction. The adjusted group mean (least squares mean) changes will be compared at a 2-sided significance level of 0.05. The *p* value along with the 95% confidence interval for the treatment difference will be reported.

6.2 Secondary Efficacy Endpoints and Analyses

Secondary efficacy endpoints will include: 1) the WOMAC pain scores at Day 5, 19, 64 and Day 94; 2) WOMAC scores on the stiffness and function subscales as well as total WOMAC score at Day 5, 19, 35, 64, and 94; 3) VAS OAKP assessments.

Data from WOMAC pain, stiffness, physical function subscales and total score, as well as VAS assessments will be listed and summarized by presenting descriptive statistics of raw data and change from baseline at each visit for each treatment group. Tabulation will be based on Study Knee and Non-study Knee.

WOMAC stiffness, function and total score reductions at Day 35 will be evaluated using the Study Knee. Change from baseline in WOMAC stiffness, function and total score on the Study Knee between each Active Treatment Arm and the Vehicle Arm at Day 35 will be evaluated using

ANCOVA model as described in Section 6.1.

The group mean reduction in OAKP score on a 100 mm VAS scale at Day 35 for each Active Treatment Arm will be compared to the Vehicle Arm using ANCOVA model as described previously.

For dose-response estimation, the difference of adjusted group mean between the 5% and the 1% Active Treatment Arms for the WOMAC pain, stiffness, function and total score at Days 35, 64 and 94 will be tested using the same method as described in Section 6.1.

